4.3 Procedures for Documenting Pregnancy during the Study

Pregnancy occurring in a female subject should be reported to [REDACTED] within 24 hours of becoming aware of the event using the pregnancy eCRF. The investigator will also: (1) notify the subject's physician that the subject may have been treated with SP-102 and (2) follow the progress of the pregnancy to term and document the outcome of the pregnancy. Pregnancy outcome information should be forwarded to sponsor [REDACTED] when available.

Any pregnancies will be followed through delivery or premature termination. If a subject becomes pregnant during the study, any complications of that pregnancy such as abortion (spontaneous or induced), premature birth, or congenital abnormality will be captured as SAEs. In the event the eCRF system is unavailable, a back-up paper Pregnancy Reporting Form will be available for site staff to complete following reporting guidelines as outlined in [Section 4.2.2](#).

5 DATA MANAGEMENT AND STATISTICAL ANALYSIS

5.1 Data Management Considerations

eCRFs will be employed for this study. Queries will be issued for any inconsistencies, omissions, and discrepancies and will be resolved by the appropriate parties. The statistical analysis of these data will be performed by the sponsor or its representative. All AEs will be coded using the latest version of the Medical Dictionary for Regulated Activities (MedDRA). Concomitant medications will be coded using the latest version of the World Health Organization Drug Dictionary. Data management details will be outlined in a separate data management plan.

5.2 Statistical Considerations

The statistical analysis will be undertaken by [REDACTED] in collaboration with Semmur.

A detailed Statistical Analysis Plan (SAP) will be finalized and signed before database lock and the code for all subjects is broken and before analysis of the study being carried out. Any deviations from the analyses described below will be included in the SAP, which will be included in the clinical study report.

5.2.1 Sample Size Justification

5.2.2 Study Data

In an effort to streamline and modernize this clinical investigation in accordance with FDA's Electronic Source Data in Clinical Investigations Guidance for Industry ([Food and Drug Administration](#)), this trial promotes capturing source data in electronic form via DDE into eCRFs. This real-time electronic data capture is intended to eliminate unnecessary duplication of data, reduce the possibility for transcription errors, encourage entering source data during subject visits, eliminate transcription of source data into an eCRF, facilitate remote monitoring of data, promote real-time access for data review, and facilitate the collection of accurate and complete data.

For data entered directly into eCRFs, the eCRF is source. If a paper transcription or separate electronic source step is used such as for subject-facing rating scales, then the paper or other electronic documentation should be retained and made available for monitoring. Study data in this protocol will be source verified only if paper transcription or separate electronic source precede eCRF DDE.

To comply with the requirement to maintain accurate case histories, clinical investigator(s) should review and electronically sign the completed eCRF for each subject before the database is locked.

All study data will be formulated into data sets to provide transparency, traceability, and integrity of trial analysis results from the collection source. Observed study data will be mapped to the Clinical Data Interchange Standards Consortium (CDISC) Study Data Tabulation Model (SDTM) and serve as the source data from the trial. All study analyses will be completed using analysis data sets that are derived from the SDTM and follow the CDISC Analysis Data Model architecture.

5.2.3 Analysis Methods

No formal statistical hypothesis testing will be performed in this study, however descriptive statistics will be presented.

Unless otherwise specified, baseline is defined as the last non-missing measurement taken prior to treatments T1 or T2 (reference start date). This includes screening or unscheduled assessments that would have been performed no earlier than 21 days before the reference start date.

In the case where the last non-missing measurement and the reference start date coincide, that measurement will be considered pre-reference, but AEs and medications commencing on the reference start date will be considered post-reference.

For vital signs parameters, an assessment performed on reference start date with time point marked as “pre-dose” will be considered as baseline.

For cortisol suppression, glucose, and white blood cell counts, baseline is defined as the last non-missing value obtained prior to T1 or T2, which is T1/T2 Day 1 pre-dose measurement.

For NPRS, baseline is defined as the last non-missing value obtained prior to T1 or T2, which is T1/T2 Day 0 measurement.

Details on definition of baseline and calculations for the change and percent change in PD values will be defined in detail in the SAP.

5.2.4 Analysis Populations

The Safety Analysis population is defined as all enrolled subjects who receive at least one SP-102 injection.

The PD Analysis population is defined as all enrolled subjects who have a T1 period baseline PD result and at least 1 postdose PD assessment result without any protocol deviations available in either T1 or T2.

The Complete Analysis population is defined as all enrolled subjects who receive only one SP-102 injection who complete T1 – Day 28 plus those subjects who receive two SP-102 injections who complete T2 – Day 28.

Protocol deviations should be collected by site and grouped into different categories, such as those who:

- Entered the study even though they did not satisfy the entry criteria;
- Developed withdrawal criteria during the study but were not withdrawn;
- Received the incorrect dose;
- Received an excluded concomitant treatment.

Major protocol violations that impact the PD analysis may lead to exclusion from the PD population. Full details regarding these will be provided in the SAP.

5.2.5 Demographic and Baseline Characteristics

Treatment groups will be compared with respect to subject demographics and baseline characteristics and will be summarized using descriptive statistics, but no formal statistical analysis testing will be performed.

5.2.6 Pharmacodynamic Endpoints

- Dexamethasone-induced HPA suppression as measured by:
 - Observed total blood cortisol levels, change from baseline cortisol levels, and percent change from baseline cortisol levels
 - Observed glucose levels, change from baseline glucose levels, and percent change from baseline glucose levels
 - Observed white blood cell counts, change from baseline white blood cell counts, and percent change from baseline white blood cell counts
- NPRS (average leg pain and back pain) and BPI-SF
- Change from T1 Day 0 and T2 Day 0 through Day 28 in NPRS (average leg pain and back pain) and BPI-SF over time following the index (T1) and repeat (T2) epidural injections, respectively
- Percent change from T1 Day 0 and T2 Day 0 through Day 28 in NPRS (average leg pain and back pain) and BPI-SF following the index (T1) and repeat (T2) epidural injections, respectively

5.2.7 Pharmacodynamic Analyses

All PD analyses will use the PD population as the primary analysis population.

Cortisol levels, WBC counts, and fasting blood glucose levels (observed, change from baseline, and percent change from baseline) will be summarized by treatment and measurement time using descriptive statistics. Dexamethasone-induced HPA suppression will be evaluated by using the observed total plasma cortisol level, blood glucose levels, and WBC count. Other PD analyses may be performed as appropriate. For these PD endpoints, the pre-dose morning values will be determined for each subject as a Baseline for each treatment and the data will be presented as observed value, change from baseline, and as a percent of Baseline value.

The following pain-score endpoints will be summarized over time by treatment using descriptive statistics:

- NPRS (average leg pain and back pain) and BPI-SF
- Change from T1 Day 0 and T2 Day 0 through Day 28 in NPRS (average leg pain and back pain) and BPI-SF over time following the index (T1) and repeat (T2) epidural injections, respectively
- Percent change from T1 Day 0 and T2 Day 0 through Day 28 in NPRS (average leg pain and back pain) and BPI-SF following the index (T1) and repeat (T2) epidural injections, respectively

For blood cortisol and glucose levels, and WBC counts (change-from-baseline), PD parameters, ie, area under the effect curve over 28 days (AUEC_{28 days}) and maximum effect (E_{\max}) following the T1 (index) and T2 (repeat) injections will be calculated.

AUEC_{28 days} is defined as the change from baseline (for cortisol, glucose, and WBC) and calculated using linear trapezoidal summation from pre-dose to Day 28 in each treatment period. E_{\max} is the baseline-adjusted maximum increase in glucose level and WBC count or the maximum decrease in cortisol levels over the 28 days post dose in each treatment period.

The PD parameters will be analyzed using a mixed model analysis of variance using PROC MIXED with a fixed effect for treatment and a random effect for subject. Estimates and 90% confidence intervals (CIs) will be first constructed in the logarithmic scale. By taking anti-logarithms, estimates and CIs for the geometric means and ratios of geometric means will be calculated. All CIs will be 2-sided.

A lack of effect of repeat injection on the PD will be concluded if the 90% CIs for the ratio of T2 (repeat injection; Test) to T1 (index; Reference) for both AUEC_{28 days} and E_{\max} are completely contained within the range of 80 to 125%.

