2.2 Secondary Objectives

The secondary objectives of the study are to:

- Evaluate the safety and tolerability of single and repeat dose SP-102 (10 mg dexamethasone) administered by epidural injection in subjects with lumbosacral radiculopathy.
- Evaluate the analgesic effect on leg pain (as measured by the Numeric Pain Rating Scale [NPRS] in the affected leg) following the index (Treatment [T] 1) and repeat (T2) injections.

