 11. Chronic use (ie, more than 5 consecutive days) of oral or parenteral steroid medication during the 2 months prior to the Screening Visit and any oral or parenteral steroid medication in the 2 weeks prior to the Screening Visit or to the Baseline Visit.
 12. Regular use of high dose opioids (> 30 mg morphine equivalents for more than 2 days per week) in the 30 days prior to the Screening Visit ([Appendix C](#)). The subject must agree to discontinue all opioids prior to the Screening Visit.
 13. An epidural steroid injection for the treatment of the current episode of lumbosacral radicular pain during the 2 months prior to the Screening Visit.
 14. History of spine surgery prior to the Screening or Baseline Visit, which may interfere with IL epidural injection, or plans to undergo spine surgical intervention while in the study.
 15. Has donated blood exceeding 500 mL during the 45 days before Baseline Visit.
 16. Use of any investigational drug or device within 30 days prior to the Screening Visit or is scheduled to receive an investigational drug other than study drug during the course of this study.

17. If female, are lactating/breastfeeding, plan to breastfeed, currently pregnant, or plan to become pregnant while participating in the study.
18. Alcohol dependence, drug abuse, or drug addiction within 1 year of the Screening Visit.
19. Involvement in an ongoing worker's compensation claim, disability claim, or litigation related to any pain problem, receiving payments for a settled claim, awaiting pending payment for a settled claim, or any secondary gain in the opinion of the investigator.
20. The presence of any disorder, condition, laboratory abnormality, or circumstance (with the exception of the condition under study) as determined by a medical and psychiatric history, medical examination, electrocardiogram (ECG), serum chemistry, hematology, and urinalysis that, in the opinion of the investigator, has the potential to compromise subject safety, prevent study completion, and/or to have a confounding effect on outcome measures.

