7.11 Pharmacodynamic Analyses

All comparisons between treatments will be analyzed in log scale but will be reported as ratios with 90% confidence intervals for the difference. All PD analyses will use the PD Analysis population as the primary analysis population.

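### Leg-pain and BPI-SF results take as their primary set a PD population built for the blood markers, from which a subject may be removed for a treatment taken because relief was poor

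*Protocol*

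**What the plan says.** Analgesia is a stated secondary objective (Protocol 2.2): "Evaluate the analgesic effect on leg pain (as measured by the Numeric Pain Rating Scale [NPRS] in the affected leg"), after the index and repeat injections. Protocol 5.2.6 and SAP 4.1 list the pain scores among the pharmacodynamic endpoints: "NPRS (average leg pain and back pain) and BPI-SF".

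The analysis set for that class of endpoint is fixed in Protocol 5.2.7, "All PD analyses will use the PD population as the primary analysis population", and in SAP 7.11, "All PD analyses will use the PD Analysis population as the primary analysis population". The pain summaries fall within those sections (SAP 7.11.2 for NPRS, 7.11.3 for BPI-SF).

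Protocol 5.2.4 defines the PD population by a T1 baseline PD result and "at least 1 postdose PD assessment result without any protocol deviations available in either T1 or T2". The same section lists deviation categories, one of which is "Received an excluded concomitant treatment", and adds that "Major protocol violations that impact the PD analysis may lead to exclusion from the PD population". It leaves the details to the SAP. SAP 7.1.3 repeats the sentence, and SAP 7.6 says only that deviations will be adjudicated as major or minor and listed. The readable SAP gives no criteria and no timing for that judgement.

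Two other sets exist. The Safety Analysis population (everyone injected at least once) is assigned to disposition, baseline and safety tables (SAP 7.5, 7.7, 7.12). The Complete Analysis population (SAP 7.1.4) is defined by completion of Day 28, with no deviation clause, and the readable text assigns no analysis to it.

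**The concern.** One population serves two kinds of endpoint, and the same exclusion means different things for each. For cortisol, glucose and WBC, removing a subject who took another steroid protects the measurement. For pain, taking an excluded analgesic or steroid after the injection can be a consequence of poor relief. Removing that subject then conditions the analysis set on the outcome being measured.

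If the subjects removed did worse than those retained, the mean NPRS and BPI-SF changes look better than they were among everyone injected. The study has a single arm, so no comparator loses subjects in the same way, and with about 12 completers one or two removals move the mean visibly. The study is also open-label and the timing of adjudication is not given, so pain results may already be known when a violation is called major. SAP 7.11.2 and 7.11.3 contain no rule for scores recorded after an excluded treatment.

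**Working it through.** The plan gives no effect size, SD or expected rate of excluded-treatment use for pain, and Protocol synopsis and SAP 5 say that no power calculation was made. There is no stated figure to reproduce. The check is a reading of the population rules followed by an illustration of size.

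**Route from the rule to the pain result**

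1. Pain scores are PD endpoints (Protocol 5.2.6, SAP 4.1), so their primary set is the PD population (Protocol 5.2.7, SAP 7.11).
2. The membership clause can be read in two ways. At result level, one deviation-free post-dose result in either period is enough. NPRS is scheduled on Days 1 to 5, 8, 15 and 28 (SAP 7.11.2), so a subject with clean early results who later takes an excluded drug stays in. At subject level, any deviation takes the subject out.
3. Under either reading, the major-violation sentence allows discretionary removal, and receipt of an excluded treatment is a category to which it could be applied.
4. The readable text names no other set for pain.

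**Illustration (all inputs assumed)**

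Let N be the number of subjects, k the number removed, d the mean change in those retained and c the mean change in those removed.

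- Mean over all subjects: m = [(N − k)d + kc] / N
- Mean reported after removal: d
- Overstatement of the reduction: d/m − 1

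Take N = 12, the planned number completing both injections (SAP 5), and d = −3.0. For k = 2 and c = 0, m = (10 × −3 + 0)/12 = −2.50, and −3.0/−2.50 − 1 = 20%. The full set is:

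| Mean change in those removed (c) | m for k = 1, 2, 3 | Overstatement for k = 1, 2, 3 |
|---|---|---|
| +1 (worse) | −2.67, −2.33, −2.00 | 13%, 29%, 50% |
| 0 | −2.75, −2.50, −2.25 | 9%, 20%, 33% |
| −1 | −2.83, −2.67, −2.50 | 6%, 13%, 20% |
| −2 | −2.92, −2.83, −2.75 | 3%, 6%, 9% |
| −3 | −3.00, −3.00, −3.00 | none |
| −4 | −3.08, −3.17, −3.25 | −3%, −5%, −8% (understated) |

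When c = 0 the factor is N/(N − k), whatever the value of d.

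The T1 denominator may exceed 12, because enrolment continues until 12 subjects have had both injections. With an assumed 16 subjects in T1 and c = 0, the factors are 16/15, 16/14 and 16/13, that is 7%, 14% and 23%.

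**The case against.** A reader might infer three stronger things, and the documents do not support them.

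*Pain is analysed only in the PD population.* Both documents call it the primary set. A Complete Analysis population exists and the SAP list of tables is redacted, so a supportive pain table in that set cannot be ruled out. This stands, although such a table would leave the primary pain summary as it is.

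*Anyone who takes an excluded drug is dropped.* Removal is discretionary and limited to major violations that affect the PD analysis, and one clean early result may be enough for membership. The mechanism also needs drugs taken for poor relief to be prohibited after dosing. The rescue and prohibited-medication lists (Protocol 3.4.7, 3.4.8.3) are redacted, and the section on allowed medications shown in the contents cannot be read. Some analgesic use may be permitted and so be no deviation. Exclusion 12, "The subject must agree to discontinue all opioids prior to the Screening Visit", and exclusion 11 on steroids govern use before Screening or Baseline; they do not show what is prohibited after the injection. The redactions are not a fault of the plan, but they leave the likelihood of removal unknown.

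*The bias always favours the product.* A subject who took another analgesic or steroid may record better scores because of it. The table shows the bias shrinking, vanishing and reversing as c falls.

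It is also fair to say that pain is secondary and descriptive, with no test or decision rule, and that pain change in an open-label single-arm study is uncontrolled in any case. Excluded subjects with reasons (SAP 7.1) and all deviations (SAP 7.6) will be listed, so a removal would be visible. These points limit the consequence. They do not make a set built for blood markers the right one for pain.

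**Conclusion.** The point holds as a possibility that the plan leaves open. The primary pain summaries use a set from which a subject may be removed for an event that can itself follow from poor pain relief, and the readable SAP adds no criteria to prevent this.

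Its size cannot be known from the documents. Under the assumed inputs it runs from a 50% overstatement (three removed, each worse by 1 point) through zero (those removed improved as much as those retained) to a small understatement. The direction rests on the assumption that those removed had less relief than those retained; the occurrence rests on removal being exercised and on the redacted drug lists. The primary objective on the blood markers and the 80–125% conclusion are not affected. This is an inexpensive improvement to a secondary, descriptive result.

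**What to change.** In Protocol 5.2.7 and SAP 7.11.2 and 7.11.3, make the Safety Analysis population the set for NPRS and BPI-SF: all injected subjects, summarised by injection received, with those who took an excluded treatment kept in. Add one pre-specified sensitivity summary in which scores after an excluded analgesic or steroid are set to that period's Day 0 value. Keep the PD population for cortisol, glucose and WBC.

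The cost is wording in both documents and one additional pain summary from data already collected. The downside is that some retained scores will partly reflect the other drug; the sensitivity summary is there to show how much that matters. No clinical rule changes.

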5.2.8 Safety Analyses

Safety endpoints are as follows:

- Incidence of treatment-emergent adverse events (TEAEs) and SAEs
- Change from baseline in clinical laboratory parameters, vital sign measurements, ECG findings, physical examination, general neurological examination findings, and targeted neurological examination findings following each treatment

5.2.8.1 Adverse Events

All AEs will be coded using the most current version of MedDRA. TEAEs and SAEs will be summarized descriptively for each treatment.

5.2.8.2 Laboratory Data

Mean changes from Baseline at each post-baseline time point for each laboratory variable will be presented. In addition, each reading will be classified as below, within, or above normal range, based on ranges supplied by the laboratory used. Shift tables for the Baseline and follow-up measurements will be presented.

5.2.8.3 Vital Signs

Summary statistics for the absolute vital sign value and the changes from Baseline will be presented by treatment group for each visit, for each of the following vital signs:

- Systolic blood pressure (mmHg)
- Diastolic blood pressure (mmHg)
- Heart rate (bpm)

Vital sign values will be categorized into the following potential clinical concern categories if applicable and summarized.

Vital Sign	Potential Clinical Concern Categories
Systolic blood pressure	≥ 160 mmHg
Diastolic blood pressure	≥ 100 mmHg
Heart rate	< 60 or > 100 bpm

5.2.8.4 Electrocardiographic Data

A listing of 12-lead ECG parameter results will be presented. Shifts in ECG parameters will be summarized by treatment group from Screening to each post dose visit at which ECG assessments are obtained.

5.2.8.5 Physical Examination Findings

Shifts in physical examination findings will be summarized by treatment group from Screening to each post dose visit at which a physical examination was performed.

5.2.9 Interim Analyses

No interim analysis is planned for this study.

6 STUDY MANAGEMENT

6.1 Ethics and Consent

6.1.1 Regulations and Guidelines

The study will be performed in accordance with this protocol, US investigational new drug (IND) regulations (21 CFR 312), ICH guidelines for Good Clinical Practice (GCP) (ICH-E6-1996), the regulations on electronic records and electronic signature (21 CFR 11), and the most recent guidelines of the Declaration of Helsinki.

6.1.2 Institutional Review Board/Independent Ethics Committees

Conduct of the study must be approved by an appropriately constituted IRB. Approval is required for the study protocol, protocol amendments, ICFs, subject information sheets, and advertising materials. No IP will be shipped to a site until written IRB authorization has been received by the sponsor or its representative.

6.1.3 Informed Consent

For each trial subject, a written ICF will be obtained before any protocol-related activities. As part of this procedure, the investigator or a designated representative must explain orally and in writing the nature, duration, and purpose of the study, and the action of the IP in such a manner that the subject and (if applicable) appointed guardian are aware of the potential risks, inconveniences, or adverse effects that may occur. Subjects should be informed that they may withdraw from the study at any time. They will receive all information that is required by federal regulations and ICH guidelines. The principal investigator or a designated representative will provide the sponsor or its representative with a copy of the IRB-approved ICF before the start of the study.

